**SECTION E - SEXUAL HISTORY**

**READ and HEARD:** Now, we want to ask about the people you have had sex with and your sexual partners. We understand that these questions are about intimate and private matters, which could make you uncomfortable. Please keep in mind that the questions are part of a scientific study, and the researchers will keep your responses confidential. Your individual responses will not be known by SANBS. Please answer these questions to the best of your knowledge and as truthfully as you can.

E1. Do you consider yourself to be? (Choose one)

- 1        Straight/heterosexual
- 2        Bisexual
- 3        Gay/homosexual
- 97       Don't Know
- 98       Refuse to Answer

**READ and HEARD:** The following questions will ask you about your sexual experiences. In these questions, include only those people you have had oral, vaginal, or anal sex with. Do not include people that you have only kissed. Please try to be as accurate and honest as possible. If you cannot remember the precise answers below, please provide your best estimates.

**Please note:** For the next few questions the terms “sexual contact” and “sex” refer to any of the following activities, whether or not a condom or other protection was used:

1. **Vaginal sex (contact between penis and vagina)**
2. **Oral sex (mouth or tongue on someone’s vagina, penis, or anus)**
3. **Anal sex (contact between penis and anus)**

E2a. (Ask of Men Only) How many different women have you had sex with since you first began having sex?

— — — —

- 9997        Don't Know
- 9998        Refuse to Answer
- 9999        Not Applicable

E2a.1 **If Answer is Don't Know, Else Skip.** If you Don't Know, can you give an approximate answer? \_\_ \_

E2b. (Ask of Men Only) How old were you when you had sex with a woman for the first time?

\_\_ \_

9997 Don't Know

9998 Refuse to Answer

9999 Not Applicable

E3a. (Ask of Men Only) How many different men have you had sex with since you first began having sex?

\_\_ \_ \_\_ \_

9997 Don't Know

9998 Refuse to Answer

9999 Not Applicable

E3a.1 **If Answer is Don't Know, Else Skip.** If you Don't Know, can you give an approximate answer? \_\_ \_

E3b. (Ask of Men Only) How old were you when you had sex with a man for the first time?

\_\_ \_

9997 Don't Know

9998 Refuse to Answer

9999 Not Applicable

E2a. (Ask of Women Only) How many different men have you had sex with since you first began having sex?

— — — —

9997 Don't Know

9998 Refuse to Answer

9999 Not Applicable

E2a.1 **If Answer is Don't Know, Else Skip.** If you Don't Know, can you give an approximate answer? \_\_ \_

E2b. (Ask of Woman Only) How old were you when you had sex with a man for the first time?

— — — —

9997 Don't Know

9998 Refuse to Answer

9999 Not Applicable

E3a. (Ask of Women Only) How many different women have you had sex with since you first began having sex?

— — — —

9997 Don't Know

9998 Refuse to Answer

9999 Not Applicable

E3a.1 **If Answer is Don't Know, Else Skip.** If you Don't Know, can you give an approximate answer? \_\_ \_

E3b. (Ask of Women Only) How old were you when you had sex with a woman for the first time?

— — — —

- 9997 Don't Know
- 9998 Refuse to Answer
- 9999 Not Applicable

E4a. Have you ever been physically abused, physically assaulted, or beaten by a sexual partner?

- 0 No **Skip to E5**
- 1 Yes
- 7 Don't Know
- 8 Refuse to Answer

E4b. In the six months before your donation were you physically abused, physically assaulted or beaten by a sexual partner?

- 0 No
- 1 Yes
- 7 Don't Know
- 8 Refuse to Answer

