#### **4.7 Data Management**

The specifics of at least four data management systems will need to be developed by the REDS-III DCC, Research Triangle Institute:

1. Tracking system. SANBS is currently developing an operational tracking system for notification and counseling of donors with positive viral test results which will serve to identify potential participants. The specifications for that tracking system are included as **Appendix 6**. This document can serve as guide to the components that are necessary for a tracking system. In addition, a web-based Study Management System (SMS) will be designed to monitor enrollment of cases and controls, completion of questionnaires, blood sampling tasks and other required visit procedures for each enrolled participant in Objectives 1 and 2 and at follow-up visits for those enrolled in Objective 3. More specifically, this will require the development of a regular reporting system with which to closely monitor the demographic characteristics of cases to ensure the enrollment of properly matched controls at the specified ratio (1:3).
2. Laboratory database. Test result data for the additional laboratory testing mandated by this protocol and not part of usual SANBS procedure, will be entered into the SANBS main frame and uploaded via the supplementary file to the REDS-III South Africa HIV/HBV Biological Specimen Inventory (BSI) database.
3. Questionnaire database. ACASI interviews will be consolidated from laptops to a central database on a daily basis at SANBS using QDS Software, and then transferred weekly to RTI via a secure FTP server for QC and analysis.

4. Clinical questionnaires. Teleform forms completed at each visit during Objective 3 of the study will be scanned into a database at SANBS headquarters (Constantia Kloof), and transferred to RTI using standard procedures already in use for the REDS-III South Africa project.

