#### **4.10.1 Data Security**

Data in this study will be kept confidential, and US investigators and members of the DCC will not have access to personally identifiable information (PII). At the SANBS study sites, key study personnel will have access to records with PII. For example, written signed consent forms. Study documents with PII will be stored in secure locations separate from study data (eg. laboratory results and questionnaires). Identifying information from donors that is temporarily linkable to the laboratory results, routine donation records and our study specific-questionnaires for the

purpose of proper identification and notification of each donor will only be available to SANBS operational staff. We will take several steps to minimize the possibility of inadvertent disclosure of the identity and information of participants. First, data are tracked and linked with a donation identification number (DIN) created at the time a person donates at SANBS. In addition a donor number is created to track individuals longitudinally. For this study, none of the datasets transferred to the US will contain PII, rather the DIN and an assigned study participant identification number will be used to link the donation history, health and risk screening data, laboratory results and study specific questionnaires entered into the study database.

Limitations on who can access donor information already exist within SANBS. Only those individuals with job responsibilities that require access to PII have access to donor names and contact information. Such access is controlled through computer systems that only allow working on password protected workstations that require individual usernames and passwords. Similar restrictions on access will be in place for the study research staff.

Due to the sensitive nature of the study, the following steps are to be taken to protect the personal information of individuals recruited and/or enrolled in the study. The goal of this security plan is to put in place procedures that will reduce the risk of release of personal or sensitive information related to the study participants. The below items are the key points to achieve data security and participant privacy during the study period.

- Require the use of a two-factor authentication process to access the study management system (SMS).
- Store study materials in access-controlled rooms (use of key or access card to gain entry)

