**Blood Donor Risk Factor Study Questionnaire (English)**

**SECTION A – GENERAL STUDY DATA**

**This section is to be completed by the research assistant or other research staff.**

A1. Participant ID (*Internal study number to be assigned by Study Management System*)

\_\_\_\_\_

A2. Participant donor number (*Number that will link with donor’s Meditech info*)

\_\_\_\_\_

- 97      Don't Know
- 98      Refuse to Answer
- 99      Not Applicable

A3. Blood collection site. (*Blood collection site neumonic (clinic site code). The neumonic can be mapped back to Branch, Zone or Province – this will have to be coded during analysis phase*)

\_\_\_\_\_

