**SECTION B - DEMOGRAPHIC DATA**

**APPEARS ON SCREEN and HEARD if ACASI: This study has been approved by Ethical Committees in South Africa and the USA. This study also has been approved by the Office of Management and Budget; OMB XXXX, OMB approval expires XX, XXXX, 201X.**

**APPEARS ON SCREEN and HEARD if ACASI: We are asking you to respond as truthfully as you can. Please keep in mind that the questions are part of a scientific study, and the researchers will make every effort to keep your responses confidential. However, there is a small chance that your responses may not be kept confidential, but your name is not collected on the questionnaire and your responses cannot be easily traced back to you. Please answer these questions to the best of your knowledge and as truthfully as you can. You may skip any questions that you are not comfortable answering.**

**In this section of the questionnaire the research assistant will show you how to use the computer to answer the interview questions. After completing this section, with help from the research assistant, you will be left to complete the interview in private. If you have any questions at any time or are unsure of what to do, please ask for help.**

B1. What is your gender? (Choose one)

- |    |                  |
|----|------------------|
| 1  | Male             |
| 2  | Female           |
| 3  | Transgender      |
| 97 | Don't Know       |
| 98 | Refuse to Answer |

B2. What is your birth year?

— — — —

- |      |                  |
|------|------------------|
| 9997 | Don't Know       |
| 9998 | Refuse to Answer |

B3. What is your birth month? (Choose one)

January

February

March

April

May

June

July

August

September

October

November

December

Don't Know

Refuse to Answer

B4. What is your birth day?

97 Don't Know

98 Refuse to Answer

B5a. What is your country of birth? (Choose one)

- 1 South Africa
- 2 Zimbabwe
- 3 Malawi
- 4 Mozambique
- 5 Swaziland
- 6 Botswana
- 7 Lesotho
- 8 Namibia
- 9 Nigeria
- 10 Other
- 97 Don't Know
- 98 Refuse to Answer

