***If Study Group 3 (A7=3), Skip to Instruction After L9.***

**SECTION L - EXPOSURE AND TREATMENT**

*Study Group 1 Only (A7=1)*

**READ and HEARD:** *This is the final section of the questionnaire. It may be difficult for you to respond to these questions. Again, the responses are anonymous and will help us improve blood safety in South Africa.*

L1. Did you know your HIV status before your donation? (Choose one)

- 0 No
- 1 Yes
- 97 Don't Know
- 98 Refuse to Answer

L2. How do you think you may have become infected with HIV?

-----

L3. When do you think you may have been infected with HIV? (Year)

- \_\_\_\_\_\_ YYYY
- 2097 Don't Know (Year)
- 2098 Refuse to Answer (Year)

L4. When do you think you may have been infected with HIV? (Month) (Choose one)

- January
- February
- March
- April
- May
- June
- July
- August
- September
- October
- November
- December
- Don't Know
- Refuse to Answer

L5. Are you currently taking antiretroviral medicines, also called ARVs? (Choose one)

- 0 No
- 1 Yes skip to L7?
- 97 Don't Know
- 98 Refuse to Answer

L6. Have you taken antiretrovirals (ARVs) in the past? (Choose one)

- 0 No
- 1 Yes
- 97 Don't Know
- 98 Refuse to Answer

L7. (Ask of Women Only) If Female: Did you know you were HIV-positive prior to or during your most recent pregnancy?

- 0 No
- 1 Yes
- 96 Not applicable, never been pregnant **SKIP to After L9.**
- 97 Don't Know
- 98 Refuse to Answer

L8. (Ask of Women Only) Did you take antiretrovirals during your most recent pregnancy to try to prevent HIV transmission to your baby?

- 0 No
- 1 Yes
- 96 Not Applicable
- 97 Don't Know
- 98 Refuse to Answer

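### The questionnaire promises anonymity and that SANBS will not know the answers, but each record carries a donor number and full birth date and is held at SANBS

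*Protocol*

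**What the plan says.** **Assurances on screen (Appendix 7).** The introductions to Sections E and H both state: "Your individual responses will not be known by SANBS". Section L, headed for HIV cases only, states: "the responses are anonymous and will help us improve blood safety in South Africa". The opening screen of Section B is more careful. It says there is a small chance that confidentiality may fail, that no name is collected, and that answers are not easily traced to the respondent.

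**What the record holds (Appendix 7).** Section A includes "A2. Participant donor number", annotated as the number that links to the donor's Meditech information. It also holds the clinic code (A3) and a code for HIV case, HBV case or control (A7). Section B asks for birth year (B2), birth month (B3) and then "B4. What is your birth day" (B4).

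**Where the record goes.** Section 4.7 states: "ACASI interviews will be consolidated from laptops to a central database on a daily basis at SANBS using QDS Software". The data then go weekly to the DCC. Section 4.4.1 describes the same daily backup at SANBS and weekly upload.

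**Safeguards (Section 4.10.1).** Documents with PII are to be stored apart from study data, with questionnaires given as an example of study data. Identifying information that is temporarily linkable to the questionnaires is available only to SANBS operational staff. The DCC and US investigators are to have no access to PII, and "none of the datasets transferred to the US will contain PII"; the DIN and a study participant number do the linking instead.

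**The concern.** Section 4.10 names loss of confidentiality about HIV and HBV status and risk behaviour as the first risk to participants. The interview asks about assault, same-sex partners, drug use and jail. Respondents answer after hearing specific assurances about who will know and whether they can be identified, so those assurances should describe the data flow as the protocol writes it. If they do not, participants are misinformed about the main risk they accept. The instrument would also conflict with the data security section under which it is run.

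**Working it through.** No formula applies. The check compares each assurance with the record content and the data flow.

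1. **Anonymous (Section L).** A record is anonymous only if its holder cannot tie it to a person. Item A2 is the donor number. Section 4.4.1 identifies Meditech as the SANBS blood establishment computer system, and Appendix 6 defines the donor number as the donor's Meditech number. The same record also holds full birth date, clinic code and case group. SANBS holds both the record and the system that resolves its key. The record is coded and identifiable, not anonymous.

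2. **Not known by SANBS (Sections E and H).** The consolidated database of individual interviews sits at SANBS (Sections 4.4.1 and 4.7). Section 4.10.1 places the linkable identifying information with SANBS operational staff. No passage bars SANBS staff from the consolidated file, and none separates A2 from the answers. The on-screen statement has no qualification, and the written arrangement does not support it.

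3. **Consistency within the questionnaire.** The opening screen admits a small chance that confidentiality fails. Sections E, H and L then give assurances without that caveat. The two cannot both describe the same arrangement.

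4. **Transfer to the DCC (Section 4.10.1 against Sections 4.4.1 and 4.7).** The interview data go weekly to the DCC. The transferred identifiers that Section 4.10.1 lists are the DIN and the study participant number. The donor number and birth date are not on that list, yet both are interview fields, and no step to remove or mask them is stated. Finding a conflict here takes two assumptions: that donor number or full birth date counts as PII, and that no unstated procedure strips them. This limb is therefore weaker than the first two.

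5. **Whether the fields are needed.** Appendix 7 already builds a unique identifier by joining A3 and A1, and the study management system assigns A1. The date checks in Sections H and I compare reported years with birth year (B2) or with one another; none uses B3 or B4. A7 drives the skips in Sections K and L, and A3 carries the clinic needed for the clustering described in Section 4.8.1. So A2, B3 and B4 can go, while A1, A3, A7 and B2 must stay.

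6. **Reach.** HIV cases 300, HBV cases 150, controls up to 900: 300 + 150 + 900 = 1,350 planned interviews at most for the Section E and H statement. The Section L statement reaches about 300 HIV cases.

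**The case against.** The strongest reply has four parts.

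- **The opening screen governs.** Every respondent is first told that confidentiality is not absolute and that no name is collected. The consent forms (Appendices 2 to 4), which are not in the text reviewed, may say more. This stands as context and shows that the protocol did not set out to conceal the risk. It does not make the later sentences accurate.
- **Stored at SANBS is not the same as known by SANBS.** Section 4.10.1 restricts access to names, requires individual passwords and has study staff sign non-disclosure agreements. It does not say that operational staff read answers. This stands as far as it goes: nothing shows that anyone at SANBS would read them. The assurance is still unqualified, and the key lies in the same record as the answers.
- **The donor number may add little to the DIN.** Appendix 6 holds donor number and donation number side by side, and Section 4.10.1 openly sends the DIN to the US. It also mentions the donor number as a tracking number, and it does not say that linkage is by DIN and study number alone. This weakens the DCC limb for the donor number and leaves birth date as the clearer problem there.
- **The harm is not shown.** A reader might infer that one lost laptop would identify an HIV-positive donor. The documents do not support that: no name is collected, and resolving a donor number needs access-controlled SANBS records. A reader might also infer that donors would under-report and so bias the case-control comparison. Research staff complete Section A, respondents do not see the back-end flow, and nothing in the protocol allows such a bias to be shown or sized.

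**Conclusion.** Two statements made to participants are wrong as the data flow is written: that the responses are anonymous (about 300 HIV cases) and that SANBS will not know them (up to 1,350 interviews). Both also clash with the questionnaire's own opening screen. This rests on the instrument and Sections 4.4.1, 4.7 and 4.10.1 alone.

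The conflict with the promise of no PII at the DCC is probable but not proven, because PII is undefined and fields might be removed in procedures the protocol does not describe. A reader might take it as an established breach; the text does not go that far. Nor does the interview contain a DIN item, so the case for dropping the donor number rests on the existing A3 and A1 identifier, not on a DIN already in the file.

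This is a fault of participant information and data minimisation. It is not evidence of biased estimates. It should be corrected because it concerns the first risk the protocol names and the correction is cheap.

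**What to change.** 1. Remove A2, B3 and B4 from the interview. Keep A1, A3, A7 and B2.
2. Key the questionnaire file on the existing identifier (A3 joined to A1). Hold the link from A1 to donor number and DIN only in the access-controlled study management system, apart from the answers.
3. If the items must stay in the instrument, state in Section 4.7 that A2, B3 and B4 are stripped before transfer to the DCC.
4. Reword Sections E, H and L to say that responses are coded and confidential and are held at SANBS under restricted access, in line with the opening screen. Removing the items does not replace this step, because SANBS would still hold the link.

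**Cost.** Three items and three on-screen sentences change, with the same edits in the ethics and OMB submissions, ideally before the interview is programmed. One cross-check on mis-keyed participant numbers is lost; the study management system can supply it. Day and month of birth are no longer self-reported, and no check in the questionnaire uses them.

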**If E2a is equal to 0 and E3a is equal to 0 and B1 is equal to 1, then skip to Section H.**

**If E2a is equal to 0 and E3a is equal to 0 and B1 is equal to 2, then skip to Section H.**

E5a. Have you ever been sexually abused, sexually assaulted or forced to have any kind of sex when you did not want to?

- 0 No ***Skip to Next Section.***
- 1 Yes
- 7 Don't Know
- 8 Refuse to Answer

E5b. In the six months before your donation were you sexually abused, sexually assaulted or forced to have any kind of sex when you did not want to?

- 0 No
- 1 Yes
- 7 Don't Know
- 8 Refuse to Answer

E5c. In the six months before your donation were you sexually abused, sexually assaulted or forced to have any kind of sex when you did not want to with someone you consider to be an intimate partner, such as a spouse, husband, wife, boyfriend or girlfriend?

- 0 No
- 1 Yes
- 7 Don't Know
- 8 Refuse to Answer

**SECTION F - SOCIAL/SEXUAL MATRIX**

**READ and HEARD:** *This next set of questions is about sexual experiences you may have had. While some people have had a lot of sexual experience, others have not, so questions may or may not apply to you. Please answer these questions as accurately as possible. Remember that answers that you provide will be combined with those from all other people who complete the questionnaire and we will never disclose individual responses to any question. Specifically, we will ask about sexual activities that include vaginal, anal and/or oral intercourse. Please answer these questions to the best of your knowledge and as truthfully as you can.*

F1. How many people did you have sex with in the 12 months before your blood donation?

— —

- 97 Don't Know
- 98 Refuse to Answer
- 99 Not Applicable

**If F1 is equal to 0, then skip to instruction Section H.**

F2. How many people did you have sex with in the 6 months before your donation? **(THIS INFORMATION DOES NOT APPEAR TO THE RESPONDEN: This is the seed number for the social matrix (0 up to 5 partners in last six months - persons with more than 5 partners will only be asked about 5 partners).**

— —

- 97 Don't Know
- 98 Refuse to Answer
- 99 Not Applicable

**READ and HEARD:** *Now, we want to ask about the people you have had sex with and your sexual partners. If you had more than five partners in the 6 months before your blood donation, we are only going to ask you about the five most recent people you have had sex with and your sexual partners. Please start with the most recent person you had sex with before your blood donation and then move back in time.*

F3. What is Partner 1's gender?

- 1 Male
- 2 Female
- 3 Transgender
- 97 Don't Know
- 98 Refuse to Answer

F4. How old is partner 1?

— —

- 97 Don't Know
- 98 Refuse to Answer

F5. When did your relationship with partner 1 start? We recognize that you may not remember the exact date and so we are asking that you try to recall the month and the year.

Month \_\_\_\_\_ Year \_\_\_\_\_

- 97 Don't Know
- 98 Refuse to Answer
- 99 Not Applicable

F6a. Are you currently have sex with partner 1?

- 0 No
- 1 Yes
- 97 Don't Know
- 98 Refuse to Answer
- 99 Not Applicable

If F6a = yes, skip to F7

F6b When did your relationship with partner 1 end? We recognize that you may not remember the exact date and so we are asking that you try to recall the month and the year.

Month \_\_\_\_\_ Year \_\_\_\_\_

97 Don't Know

98 Refuse to Answer

99 Not Applicable

F7. What type of partner is partner 1? (Choose one)

1 Primary partner - Your husband, wife, boyfriend or girlfriend

2 Regular partner - Had sex with regularly, but not your primary partner (husband, wife, boyfriend or girlfriend)

3 Casual partner - Had sex more than once but not regularly

4 One time partner - Had sex only once

5 Anonymous partner - Did not know, met for sex, never plan to see again

6 Sex worker - Money or other goods were exchanged for sex

97 Don't Know

98 Refuse to Answer

F8. How would you describe partner 1's race or ethnicity? (Choose one)

- 1 Black
- 2 White
- 3 Coloured
- 4 Asian
- 6 Other
- 97 Don't Know
- 98 Refuse to Answer

F9. What country is partner 1 from?

- 1 South Africa
- 2 Zimbabwe
- 3 Malawi
- 4 Mozambique
- 5 Swaziland
- 6 Botswana
- 7 Lesotho
- 8 Namibia
- 9 Nigeria
- 10 Other
- 97 Don't Know

98 Refuse to Answer

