#### **4.1 Study Population**

We will conduct a case-control study of risk factors and molecular surveillance for incident HIV and HBV infections in blood donors in South Africa. Accrual, enrollment and follow-up is planned to occur during the period of 3 years (April 2014 – March 2017).

*Our Two Case Groups* will be: (1) 300 incident HIV infected SANBS blood donors, as established through either combined ID-NAT/serology (“NAT yield”) or LAg Avidity assay testing, and (2) 150 incident HBV infected SANBS blood donors, as established through combined ID-NAT/serology (“NAT yield”) and anti-HBc negative testing.

*Controls* will comprise a sample of up to 900 SANBS blood donors who are negative for all infectious markers for which SANBS currently tests and that (a) come from the same geographic areas as the cases (distributed across up to 5 of the 7 regional zones within SANBS) and will further be frequency matched for (b) population group (race), and (c) age. We will enroll three controls for each incident HIV case. These participants will serve as controls for HBV cases also.

*Prospective Cohort:* Approximately 50 persons with very recent HIV infection (NAT yield only) and up to 20 elite controllers identified during this study (mid-2014 – mid-2017) will also be eligible for enrollment in a six month prospective longitudinal study with samples collected for PBMC and other specimen preparations as soon possible after the index donation followed by additional specimen collection at 2, 3 and 6 months.

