### **4.4 Measurement**

#### **4.4.1 Schedule of Measurement**

**Risk Factor Questionnaire:** A new questionnaire for the South Africa setting has been developed in English from a template previously used in Brazil for the REDS-II study. It assesses risk exposure over two intervals; ever and within the 6 months preceding the index donation. **Appendix 7** provides content for the risk factor questionnaire. The interview will be an audio computer-assisted structured interview (ACASI) as done successfully in a previous REDS-II and current REDS-III study in Brazil. Participants will be able to read and hear the questions using

ear phones for privacy. Interviews will be conducted using portable laptops so as to provide ease of access to the study participants. The ACASI interview will be conducted in a private location, ideally at a SANBS blood centre, but we will allow the interview to be conducted at the study participants' location of preference, such as at home. We propose to use 10 laptop computers (2 per zone) which will permit simultaneous interviews at different locations throughout SANBS. It will take approximately 30-45 minutes to complete the questionnaire. Interview data will be backed-up from the laptops onto a server or dedicated desktop computer at SANBS central offices on a daily basis, and uploaded weekly via a secure FTP site to the Data Coordinating Centre.

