***If F1a is equal to 1 and F1b is equal to 0, then skip to Section G.***

F12. What is partner 1's HIV status? (Choose one)

- 1 Positive
- 2 Negative
- 3 Unknown
- 98 Refuse to Answer

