***READ and HEARD: The next set of questions is about your FOURTH sexual partner, BEFORE your blood donation.***

***READ and HEARD: The next set of questions is about your FIFTH sexual partner, BEFORE your blood donation.***

**SECTION G - SEXUAL PARTNER RISKS**

*If E2a is equal to 0 and E3a is equal to 0 and B1 is equal to 1, then skip to Section H.*

*If E2a is equal to 0 and E3a is equal to 0 and B1 is equal to 2, then skip to Section H.*

**READ and HEARD:** Now, we want to ask about some of the behaviors of the people you have had sex with and your sexual partners. As before when answering, please consider only the following activities, whether or not a condom or other protection was used:

1. *Vaginal sex (contact between penis and vagina)*
2. *Oral sex (mouth or tongue on someone's vagina, penis, or anus)*
3. *Anal sex (contact between penis and anus)*

**You may not know the answers to these questions. Please answer these questions to the best of your knowledge. Several of the questions refer to the period of time in the "six months before your blood donation". This means before your most recent blood donation.**

G1a. To the best of your knowledge, have you ever had sex with anyone who was an injection drug user? (Choose one)

- |    |                  |                    |
|----|------------------|--------------------|
| 0  | No               | Skip to G2a |
| 1  | Yes              |                    |
| 97 | Don't Know       |                    |
| 98 | Refuse to Answer |                    |

G1b. In the 6 months before your donation, have you had sex with anyone who was an injection drug user? (Choose one)

- |    |                  |
|----|------------------|
| 0  | No               |
| 1  | Yes              |
| 97 | Don't Know       |
| 98 | Refuse to Answer |

G2a. To the best of your knowledge, have you ever had sex with anyone who tested positive for HIV? (Choose one)

- 0 No **Skip to instruction before G4a**
- 1 Yes
- 97 Don't Know
- 98 Refuse to Answer

G2b. In the 6 months before your donation, have you had sex with anyone who tested positive for HIV? (Choose one)

- 0 No
- 1 Yes
- 97 Don't Know
- 98 Refuse to Answer

G3a. To the best of your knowledge, have you ever had sex with a man who has had sex with another man? (Choose one)

- 0 No **Skip to G4a**
- 1 Yes
- 97 Don't Know
- 98 Refuse to Answer

G3b. In the 6 months before your donation, have you had sex with a man who has had sex with another man? (Choose one)

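### Donors with lifetime partners but none in the 12 months before donation skip all of Section G, so the lifetime partner-risk items G1a to G7a are structurally missing for them

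*Protocol*

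**What the plan says.** All items are in Protocol, Appendix 7, unless stated.

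- **Section F, item F1** asks "How many people did you have sex with in the 12 months before your blood donation". The instruction that follows is "If F1 is equal to 0, then skip to instruction Section H".
- **Section G** lies between F and H. Its entry gate reads "If E2a is equal to 0 and E3a is equal to 0 and B1 is equal to 1, then skip to Section H", with a parallel line for B1 = 2. E2a and E3a are lifetime partner counts.
- **Section G items** come in pairs, one lifetime and one for the 6 months before donation. The first is "To the best of your knowledge, have you ever had sex with anyone who was an injection drug user". The lifetime items G1a to G7a cover partners who injected drugs, were HIV-positive, were men who had sex with men, had been transfused, had haemophilia, had been jailed, or had occupational blood exposure.
- **Section 4.4.1** says of the questionnaire: "It assesses risk exposure over two intervals; ever and within the 6 months preceding the index donation".
- **Section F, partner-1 block**, after item F10d, carries a second rule: "If F1a is equal to 1 and F1b is equal to 0, then skip to Section G". The instrument has no item F1a or F1b.
- **Section 4.1** plans "300 incident HIV infected SANBS blood donors", "150 incident HBV infected SANBS blood donors" and up to 900 controls, three per HIV case. Section 4.9 plans a nonresponse bias analysis, followed by reweighting, multiple imputation or both.

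**The concern.** A 12-month question decides who is asked lifetime questions. A donor whose last partner was 11 months before donation can reach G1a to G7a. One whose last partner was 13 months before cannot, even if both have the same partner history. No other section asks these lifetime items.

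This is missingness by design. If recent inactivity is commoner in controls than in recently infected cases, as seems likely, the missingness depends on case status. An analyst must then code the skipped items as 'No', drop the donors, or impute. The first can shift odds ratios and the second changes the population being compared. The third has no observed donor with F1 = 0 to learn from.

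**Working it through.** **Skip trace.** The protocol states no figure on this point, so the first check is the routing.

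| Respondent | Before E5a | After F1 | Section G gate, if reached |
|---|---|---|---|
| No lifetime partner (B1 = 1 or 2) | sent to H | not reached | would send to H |
| Lifetime partner, F1 above 0 | continues | continues through F | admits |
| Lifetime partner, F1 = 0 | continues | sent to H | would admit, but never reached |

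The third row loses G1a to G7a. The 6-month items G1b to G7b are also unasked, but for these donors the answer follows logically as 'No'.

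**Who is skipped.** Group sizes come from Section 4.1 and, for HBV, Table 9 (150 cases, 450 controls). The shares with F1 = 0 are assumptions: s1 in cases, s0 in controls.

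Share of controls among those skipped = n0·s0 / (n0·s0 + n1·s1)

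For 300 HIV cases and 900 controls:

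- s1 = 5%, s0 = 5%: 45 / (45 + 15) = 75%
- s1 = 2%, s0 = 5%: 45 / (45 + 6) = 88%
- s1 = 2%, s0 = 10%: 90 / (90 + 6) = 94%
- s1 = 15%, s0 = 5%: 45 / (45 + 45) = 50%

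The 150:450 HBV comparison gives the same percentages. With all 450 cases and 900 controls, equal 5% shares give 45 / (45 + 22.5) = 67%, and the share falls to 50% at 10% of cases against 5% of controls. If 5 to 10% of controls have F1 = 0, 45 to 90 of the 900 have no G1a to G7a data.

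**Null odds ratio if skipped items are coded 'No'.** Let p be the lifetime prevalence, equal in cases and controls and in asked and skipped donors. Let a1 and a0 be the skipped shares.

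OR = [p(1−a1) / (1−p(1−a1))] ÷ [p(1−a0) / (1−p(1−a0))]

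Example with p = 0.05, a1 = 0.02, a0 = 0.10: recorded prevalence is 0.049 in cases and 0.045 in controls, so OR = (0.049/0.951) ÷ (0.045/0.955) = 1.09.

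| Skipped, cases | Skipped, controls | OR at p = 0.05 | OR at p = 0.20 |
|---|---|---|---|
| 1% | 5% | 1.04 | 1.05 |
| 2% | 10% | 1.09 | 1.11 |
| 5% | 20% | 1.20 | 1.23 |

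**With a real association.** Assume prevalence 10% in asked controls and 18.2% in asked cases, with 10% of controls and 2% of cases skipped.

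- Dropping skipped donors: (0.182/0.818) ÷ (0.10/0.90) = 2.00.
- Coding them 'No': 0.182 × 0.98 = 0.178 and 0.10 × 0.90 = 0.090, giving 2.19.
- Full data: 2.19 if lifetime prevalence in the skipped donors is 0, falling to 1.89 if it is 15%.

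The 'No' coding is therefore right only if skipped donors truly had no such partners. Otherwise it overstates the odds ratio here.

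**The case against.** The other side has a good deal of weight.

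- **Section G's gate says little about intent.** The same two lines are already printed before E5a, so the gate may simply be redundant. Skipping partner questions after a year without a partner could be a way to shorten a 30 to 45 minute interview. This stands as to intent. It does not change what the printed route does.
- **Section 4.4.1 is a general description.** It does not promise every lifetime item to every respondent, and some items (J1, K2, K3) have no lifetime version. This also stands. The point is a mismatch with the stated aim, where lifetime items exist but are withheld on a 12-month criterion.
- **The odds ratios depend on a coding the protocol does not prescribe.** Section 4.9 plans reweighting or imputation. F1 is recorded, so the skip is visible and can be stratified on. This stands as to size, but no donor with F1 = 0 has data on these items, so imputation would be pure extrapolation.
- **Relevance is low.** The target is recent infection, none of the Section 4 hypotheses uses G1a to G7a, and HBV contact is asked in J33 to J35. A comparison limited to recently active donors could be defended, but it should be chosen and stated, not produced by a skip.
- **Appendix 7 is visibly unfinished**, with open drafting questions at J14a and L5. That is a reason to correct the routing now.

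A reader might take the F1a/F1b rule as proof that Section G was the intended destination. The documents do not support that. The items it cites do not exist, and it sits in the partner-1 block, which a respondent with F1 = 0 has already left.

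**Conclusion.** The routing fault is real and can be read directly from the printed instrument: donors with lifetime partners and F1 = 0 cannot answer G1a to G7a. That most of them are controls is an inference. It follows from the 1:3 ratio unless the F1 = 0 share in HIV cases reaches about three times that in controls (twice, over all cases), which is implausible for recent, largely sexually acquired infection.

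The consequence is minor. The range of 1.04 to 1.23 under the null rests on assumed skip shares, an assumed prevalence of 5 to 20%, equal prevalence in skipped and asked donors, and coding as 'No'. Lower prevalence in skipped donors would shrink it. Even the top value is below the detectable odds ratios of 1.65 to 1.94 in Table 8.

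Two stronger readings do not hold. One is that every lifetime partner-risk odds ratio will be inflated; that requires the 'No' coding, which the protocol does not specify. The other is that F1 alone causes the gap. G2a = 'No' jumps to G4a, so G3a is also lost for anyone who gives that answer, whatever their F1.

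**What to change.** Before the questionnaire is fielded, because the data cannot be recovered afterwards:

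1. Change the destination of F1 = 0 from Section H to the entry instruction of Section G, so that the lifetime gate decides who continues.
2. When F1 = 0, fill the 6-month sub-items G1b to G7b as 'No' without asking them.
3. Correct the G2a = 'No' skip so that it leads to G3a. Without this, rerouting F1 would still leave G3a unasked for those respondents.
4. Delete the rule citing F1a and F1b, or rewrite it to refer to items that exist.

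The cost is a few skip edits and at most seven short extra items for a small group. Sample size and planned analyses are unaffected.
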